
13.2 Statistical Analyses for Secondary Aims

Maintenance. We will compare baseline to 6- and 12-month changes in UV exposure and protection across study arms. Tests will be two-sided with a 5% type I error for these secondary analyses. We anticipate having follow-up data from approximately 960 and 768 participants at 6- and 12-months, respectively. This will allow for 154 participants in the e-pamphlet arm and 307 in each of the other two arms at 12 months. Detectable differences with 80% power are presented in Table 3.

Implementation. Using BeHealth's Wasabi data management system, we will create a summary index representing how frequently and for how long participants are logged into the interventions and how many sections are completed and determine whether this index is associated with behavioral outcomes. Whether and when a user accesses the e-pamphlet will be noted. We have experience using Google Analytics "goals" to track how frequently individual pages within modules are accessed. We will ask participants about their satisfaction with the study/intervention and selected components (e.g., the enhanced features) both from within the interventions and a one-month follow-up inquiry. These implementation variables will also be linked to participant source (i.e., skin protection organizations, Google Adwords, Facebook ads, consumer research panel) when possible so that sources can be compared in terms of participant intervention implementation. We will use the methods described for Aim 2 to compare these utilization and satisfaction measures across study arms, and Spearman's correlation to measure the level of association between implementation metrics and longitudinal changes in UV exposure and protection indexes within and across study arms. Tests will be two-sided with a 5% type I error for these secondary analyses. We anticipate 1350 participants at 1-month follow-up (epamphlet = 270, others = 540). Whether individuals click into the pages with discounts and free samples from skincare companies will be noted. We will assess whether accessing more incentives within the interventions is associated with greater intervention utilization and better behavioral outcomes.

Cost. We will estimate mean and median costs for each intervention. We will distinguish between development costs (one-time capital investment or "sunk" costs) and implementation costs, or the costs to maintain the interventions. We will also denote whether costs are related to research or intervention delivery. Analyses will distinguish between fixed costs (costs that do not vary with enrollment, e.g., server maintenance, data storage), and variable costs, which increase with additional participants. Because most costs are expected to be fixed, the mean cost per participant will be driven largely by the number enrolled. To explore costs of scale-up, we will conduct sensitivity analyses around additional dissemination efforts and higher take-up rates. We will also estimate the cost-effectiveness of UV4.me2 relative to the other conditions, calculating cost-effectiveness ratios as the difference in estimated costs divided by the difference in estimated effectiveness to determine the incremental cost per sunburn (or incident of UV exposure) averted for each intervention pair 141,142. We will also assess and estimate medical cost (e.g., OTC medication use, healthcare visits) offsets resulting from averted sunburns. To estimate longer-term cost-effectiveness, we will develop an Excel-based model to estimate qualityadjusted life year (QALY) gains associated with each sunburn (which increases melanoma risk) averted. For the cost-effectiveness modeling, we will use data from the literature on the probability of developing various forms of skin cancer as a result of sunburns and on QALY losses associated with various cancer outcomes to estimate the cost per QALY gained. Expressing cost-effectiveness as cost per QALY gained will facilitate comparison of the UV4.me2 intervention with other preventive health interventions. For all

cost-effectiveness analyses, we will perform one-way (and n-way) sensitivity analyses to examine the impact of varying input values over a plausible range.

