4.3.1 Overview of Intervention Conditions

E-Pamphlet Condition: A free non-interactive e-pamphlet ("Skin Cancer Prevention and Early Detection" from the American Cancer Society) will be accessible via our website. We chose to include a pamphlet condition for the following reasons: 1) such pamphlets are widely available to the public and used by dermatologists and primary care providers, 2) to compare the effects of our intervention to a minimal intervention, 3) to compare our effects to prior studies that used pamphlet or minimal interventions, 4) to include a standardized rather than a variable intervention, 5) we also considered using an intervention for another health issue (e.g., nutrition, physical activity, sleep) but anticipated that skin protection organizations would be less likely to participate in that case, and 6) a no-treatment condition could affect adoption and reach and could be considered unethical for those with moderate to high skin cancer risk.

Original UV4.me: UV4.me is targeted to young adults, personally tailored, and includes interactive, multimedia, and goal-setting components. It includes 12 modules with content related to a specific topic important in terms of risk or protective behaviors: Why do people tan? To tan or not to tan? Indoor tanning, UV & looks, UV & health, Skin cancer, Skin damage, Sunscreen, Shade, Clothes, Skin exams, and Sunless tanning. Several more general sections (e.g., avatar, MyStuff – a printable summary of tailored goals/recommendations) are also included. Tailoring algorithms were created to direct participants to focus on certain modules based on their responses to a few initial questions (e.g., the indoor tanning module was recommended for indoor tanners). Throughout the program, participants are asked questions and provided with tailored feedback (e.g., "Do you know people who tan? If so, how likely are they to affect your choice to tan or not?"). A number of interactive elements (e.g., videos, games) were created to encourage implementation. For example, at the end of each module, participants could choose to set a goal for the next two weeks or not (e.g., "For the next two weeks, I will not use a tanning bed.").

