4.4.2 Measures for Secondary Aims

Maintenance. Skin cancer-related behavioral outcomes (described above) will be assessed at 6 and 12 months. We will also assess maintenance of reach, intervention implementation, and cost over time.

Implementation. Using BeHealth's data management system, we will record whether, how frequently, and for how long participants logged into the interventions, how many sections are completed, use of the enhanced features, and whether these variables are associated with behavioral outcomes. Whether individuals click into the pages with discounts/free samples will be noted. Whether and when a user accesses the e-pamphlet will be noted as well. We will ask participants to give Likert ratings of their satisfaction with and perceived helpfulness of the study/intervention and selected components (e.g., the enhanced features) both from within the intervention and a one-month follow-up inquiry. The 4-item App Subjective Quality scale from the Mobile App Rating Scale will be used to assess satisfaction (a = .93) 135. We have experience using Google Analytics "goals" to track how frequently pages within modules are accessed. These implementation variables will also be linked to participant source (i.e., skin protection organizations, Google Adwords, Facebook ads, consumer research panel) when possible so that sources can be compared by participant intervention implementation.

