Cost. We will assess total and incremental costs and evaluate the cost-effectiveness of the interventions. We will first estimate costs from a payer perspective, capturing the explicit resources required to deliver the program after all start-up costs (e.g., development/programming costs) have been incurred. We will also estimate costs from a societal perspective, which includes all costs, regardless of who bears them. These will include all explicit costs as well as the implicit program costs related to participant time (i.e., opportunity costs 136. We will also denote whether costs are related to research or intervention delivery. We will collect cost data using a modified version of prior cost surveys developed by RTI 137,138 and adapted by [name] for many interventions 139,140. The surveys capture all relevant labor- and non-labor-related inputs necessary to quantify costs. We will quantify participant time spent on the intervention using data from BeHealth's system and valuing participant time using age- and sex-specific wage rates, netting out research incentive payments to participants. We will quantify labor costs as program staff time (via questionnaires) valued using actual or estimated wages. Non-labor costs will be collected using program billing records and include materials/supplies used to support program activities and costs for facilities and contracted services. To evaluate the cost-effectiveness of UV4.me2 versus UV4.me and the e-pamphlet, we will combine cost estimates with effectiveness outcomes to estimate the cost per incident of UV exposure and sunburn averted.

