Efficacy. We will compare demographics across randomization arms using chi-squares and ANOVAs for categorical and continuous data, respectively. The primary outcomes are baseline to 3-month changes in UV exposure and protection. We will use multivariable linear regression to compare the effectiveness of UV4.me2 with UV4.me, and UV4.me2 with the e-pamphlet. We will not compare UV4.me to the epamphlet because UV4.me compared to a control condition was established in the prior study. Covariates in these models will include study arm, recruitment month/season, US region, and demographic factors identified as significantly imbalanced across arms (confounders). Analyses will be performed separately for the two primary outcomes. Variance stabilizing transformations may be applied as needed. Hypothesis tests will be two-sided with a 1.25% Type I error to account for multiple testing (2 intervention comparisons x 2 outcomes). Based on our data, experience, the enhanced study procedures, and the consumer research panel's experiences with young adults, we anticipate attrition of approximately 20% at each time-point. With 1500 young adults at baseline, we anticipate collecting 3-month follow-up data from 1200 participants, with 240 from the e-pamphlet arm and 480 participants from each of the other arms. The means (SDs) of the baseline to 3-month changes in UV exposure and protection indexes from the prior study control arm were 0.34 (0.74) and -0.37 (0.90), respectively. Given these parameters, we will have 80% power to detect small standardized effect sizes of 0.22 between the UV4.me2 and UV4.me arms, and 0.26 between the UV4.me2 and the e-pamphlet. These correspond to small detectable differences between intervention arms of 0.16 and 0.19 in baseline to 3-month changes in UV exposure and protection indexes, respectively. We will be able to detect slightly larger differences when the UV4.me2 and e-pamphlet arms are compared (detectable differences - UV exposure: 0.20; protection: 0.24). Analyses will assume that missingness depends on observed data (i.e., missing at random; MAR) 141. For drop-outs, the reason for attrition will be analyzed if available to search for evidence of informative missingness. Baseline variables will be compared by whether participants drop out or not. Significant variables will be added to the model to strengthen our MAR assumption. As a sensitivity analysis, we will use a shared parameter model with the assumption of missing not at random 142. If large changes in parameter estimation are found, we will use the results from the shared parameter model.

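### The utilisation index counts sections completed, but no sections are described for the e-pamphlet, so its contrast with UV4.me2 and the pooled correlation partly reflect format

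*Combined protocol and SAP*

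**What the plan says.** Under Implementation, Section 13.2 will "create a summary index representing how frequently and for how long participants are logged into the interventions and how many sections are completed" and relate that index to behavioural outcomes. It continues that the Aim 2 methods will be used to "compare these utilization and satisfaction measures across study arms". Section 13.1 defines the Aim 2 comparisons: the regression will "compare the effectiveness of UV4.me2 with UV4.me, and UV4.me2 with the e-pamphlet", and UV4.me versus the e-pamphlet is expressly left out. Section 13.2 also plans Spearman correlations between implementation metrics and changes in UV exposure and protection, both inside each arm and pooled over arms. These tests are two-sided at 5%.

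Section 4.3.1 gives UV4.me 12 modules plus some general areas. It describes the comparator as "A free non-interactive e-pamphlet" reached through the study website, and mentions no modules or sections for it. On recording, Section 4.4.2 lists login frequency, login duration and sections completed for the interventions, then adds: "Whether and when a user accesses the e-pamphlet will be noted as well". Neither section says how an e-pamphlet participant is scored on sections completed, or takes that arm out of the index comparison.

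**The concern.** One of the three components of the index has no described counterpart in the e-pamphlet arm. A participant who reads the whole pamphlet has no stated way to score on it. The plan does not say whether that component is zero, missing, or counted as one section, and none of these makes the index comparable with an arm offering 12 modules. A UV4.me2 versus e-pamphlet difference could then be reported as better implementation when part of it only reflects that one product is divided into modules and the other is not.

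The second consequence matters more, because a stated hypothesis depends on it. Hypothesis 4 (Section 2.3) says that greater utilisation goes with better behavioural outcomes. If the index is lower in the e-pamphlet arm by format, and outcomes are also worse in that arm because of the assigned treatment, pooling the arms produces a positive correlation even when use and outcome are unrelated within every arm. Engagement is then confounded with assignment.

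**Working it through.** The plan states no figure for this comparison, so the check starts with its related figures, then asks how large the format effect could be.

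**1. The plan's own figures.** For two arms the detectable standardised difference is d = (z for alpha + z for power) × √(1/n1 + 1/n2).
- Aim 2, two-sided 1.25%, 80% power: (2.498 + 0.842) × √(2/480) = 0.216 for 480 vs 480 (stated 0.22). For 480 vs 240, 3.339 × √(1/480 + 1/240) = 0.264 (stated 0.26). Both reproduce.
- One-month sample: 1500 × 0.90 = 1350, split 2:2:1 into 540/540/270, as Section 13.2 states.

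**2. What the utilisation comparison can detect.** Two-sided 5%, 80% power, 1.960 + 0.842 = 2.802.
- UV4.me2 vs UV4.me, 540 vs 540: 2.802 × √(2/540) = 0.17 SD.
- UV4.me2 vs e-pamphlet, 540 vs 270: 2.802 × √(1/540 + 1/270) = 0.21 SD. If system logs cover everyone randomised, 600 vs 300, it is 0.20 SD.

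**3. The sections component alone.** Section 1.0 reports that 68% of those randomised to UV4.me in the prior trial accessed it and completed at least one module. If UV4.me2 did the same and the e-pamphlet can score only zero, the split is 0.68 × 540 = 367 of 540 against 0 of 270. That is 68 percentage points by construction, with power of essentially 100%.

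**4. The whole index under equal engagement.** The combination rule is not stated, so an equal-weight average of z-scores was assumed: index = (z logins + z time + z sections)/3. Each participant had latent engagement e ~ N(0,1), with the same distribution in all arms. Access was about 70%. Among those with access, logins = 1 + Poisson(exp(0.3 + 0.4e)), time = exp(2.5 + 0.5e + 0.5 × noise), and sections were Binomial(12, logistic(0.8e)). All three were zero without access. Sections were set to zero in the e-pamphlet arm. Arms were 540/540/270, with 400 runs per setting.
- Pamphlet logins and time logged exactly as in the web arms: UV4.me2 minus e-pamphlet = 0.53 to 0.54 SD. Logins and time have the same distribution in all arms here, so the whole difference comes from sections.
- Only access logged for the pamphlet (a scenario that the documents do not state): about 1.34 SD.

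**5. The pooled Spearman test.** The outcome was generated independently of engagement within every arm.
- No arm effect: pooled rejection at 5% was 5.75% (time logged) and 5.25% (access only), about nominal.
- E-pamphlet outcomes 0.26 SD worse than in both web arms: pooled rejection was 14.25% (time logged) and 27.5% (access only), against 4.25% and 4.75% within UV4.me2. The Monte Carlo standard error of the 14.25% is √(0.1425 × 0.8575/400) = 1.7 points.
- The mean pooled correlation was small: 0.022 and 0.036.

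The inflation thus needs both the format difference and a real arm effect. The trial is designed to find such an effect, and 0.26 is its own detectable difference for this pair.

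**The case against.** The strongest reply is that this is a secondary analysis. No hypothesis is attached to the arm difference in utilisation. The stated purpose of the index is its association with outcomes, within-arm correlations are already planned, and the plural measures in Section 13.2 leave room for component-level and satisfaction comparisons. All of that is true and limits the stakes. It does not remove the gap: the index is among the measures to be compared, the Aim 2 methods include the e-pamphlet contrast, and the pooled correlation feeds Hypothesis 4.

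Three stronger readings are tempting, and the documents do not support them.
- A reader might infer that only access is recorded for the e-pamphlet. Section 4.4.2 adds that measure to the login records for the interventions; it does not replace them. Section 4.3 has participants told that every condition is an online intervention, and Section 4.5 offers the first-login payment in each condition. Logins and time may well be logged in all arms.
- A reader might infer that the participant-time cost is an artefact. Section 4.4.2 says: "We will quantify participant time spent on the intervention using data from BeHealth's system". Sections completed do not enter that quantity, and no text says pamphlet time is zero or missing. It bears only on the societal perspective, and Section 13.2 promises sensitivity analyses over input ranges.
- A reader might infer that UV4.me2 versus UV4.me is also unfair because UV4.me2 has more features. Section 1.0 defines implementation as the person's use of the intervention, Section 4.3.1 expects the enhancements to raise it, and Section 4.4.2 already records use of the enhanced features. Nothing says the new features count as sections. Total use of each package is a legitimate contrast.

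**Conclusion.** The concern holds for two analyses: the index contrast of UV4.me2 with the e-pamphlet, and the utilisation-outcome correlation pooled over arms. Followed as written, the first is partly determined by format and the second confounds engagement with assignment. With pamphlet logins and time logged, the simulated format effect on the index is about 0.5 SD, more than twice the 0.21 SD detectable difference. The pooled test's false-positive rate rises to about 14% when the arms differ by 0.26 SD.

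These sizes rest on an assumed equal-weight index, 70% access, 12 sections, a zero section score for the pamphlet and the stated simulation model. The direction for the index needs only a positive weight on sections and no section credit in the e-pamphlet arm. That the pamphlet has no sections is a sound inference from its description, not a statement in the plan. UV4.me2 versus UV4.me, the satisfaction comparisons and the within-arm correlations in the two web arms stand as planned, and no fault in the cost analysis is established.

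**What to change.** Amend the Implementation paragraph of Section 13.2 in three places.
1. Limit the comparison of the sections-based index to UV4.me2 versus UV4.me.
2. Compare UV4.me2 with the e-pamphlet only on measures that exist in both arms: any access, time to first access, login count and time if these are logged for the pamphlet, and satisfaction.
3. For Hypothesis 4, use within-arm Spearman correlations, or a correlation stratified by arm, in place of the pooled one.

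This costs wording only and needs no new data. The web-arm comparison can still detect 0.17 SD with 540 per arm, and the common-measure contrast with the e-pamphlet 0.21 SD. The downside is that there is no comparison of the full index with the e-pamphlet arm, and each within-arm correlation uses fewer participants than the pooled one.

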2.3 Hypotheses

Hypothesis 1. We hypothesize that the study enrollment rate will be greater than in the original UV4.me efficacy study and that our sample will be representative of national demographics of young adults other than race/ethnicity (associated with skin cancer risk), indicating potential generalizability.

Hypothesis 2. We hypothesize that the UV4.me2 will be the most effective intervention, followed by UV4.me.

Hypothesis 3. We hypothesize that maintenance outcomes will be best in the UV4.me2 group, next best for UV4.me, and least for the e-pamphlet group.

Hypothesis 4. We hypothesize that greater intervention utilization (e.g., logins, module completion) and satisfaction will be associated with better behavioral outcomes

Hypothesis 5. We hypothesize that UV4.me2 and UV4.me will have higher incremental costs than the epamphlet. However, because UV4.me2 and UV4.me are also expected to result in better behavioral outcomes, we will assess cost-effectiveness to address whether these interventions are worth the additional costs.

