Randomized Controlled Trial. RCT participants will complete a baseline survey focusing on exposure and protection behaviors that takes a maximum of approximately 15 minutes on average. The study statistician will create a randomization scheme to randomize enrolled participants on a 2:2:1 basis to either the UV4.me2, UV4.me, or the e-pamphlet condition, respectively. Participants will not be informed of the differences in the intervention conditions beyond that they will all be online skin cancer risk

reduction interventions. Participants will then be asked to complete follow-up assessments at 3, 6, and 12 months post-baseline.

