Reach. We will assess eligibility and enrollment overall and by recruitment source (i.e., skin protection organizations, Google Adwords, Facebook ads, consumer research panel, word of mouth) over 12-18 months in order to assess reach/potential generalizability. Sources will be tracked by placing a unique identifying pixel in each of our authorized web ads so that we know when an individual referred from a pre-specified source accesses the study website. Additionally, we will query participants as to how they found out about the study to identify informal word of mouth diffusion (e.g., unpaid study Facebook page, earned media). The number of individuals who click on the web ads, access the study homepage, complete a screening form, are eligible/ineligible, and use the website without enrolling will be assessed. Organizational sources will be monitored and queried as to strategies (i.e., posting the study URL on their website, additional promotion) used to encourage individual participation. As we have previously, we will use Google Analytics to observe user characteristics and behavior in aggregate in terms of internet source including diffusion via word of mouth, geographic location, technology used (i.e., mobile or not), eligibility/enrollment rates, and so on. We will ask organizations to set up or allow us to set up a Google Analytics "goal" to assess such user characteristics and behavior in terms of individuals accessing the study ad from within the organization's website. We will also query organizations about their number of users/members and website views if they are monitoring these.

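### The Hypothesis 4 usage-outcome correlations at 3 and 6 months omit the season and region adjustment that section 13.1 applies to the 3-month change scores

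*Combined protocol and SAP*

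**What the plan says.** Hypothesis 4 (section 2.3) predicts that "greater intervention utilization (e.g., logins, module completion) and satisfaction will be associated with better behavioral outcomes". The Implementation paragraph of section 13.2 gives the method, to be applied both inside each arm and with arms combined: "Spearman's correlation to measure the level of association between implementation metrics and longitudinal changes in UV exposure and protection indexes". It names no covariate, partial version or seasonal stratum, does not say which visits are meant, and sets a two-sided 5% test.

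The same paragraph does refer to the regression approach, but for a different question: "We will use the methods described for Aim 2 to compare these utilization and satisfaction measures across study arms". That sentence covers differences in use and satisfaction between arms. It does not cover the link between use and outcome.

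For efficacy at 3 months, section 13.1 states: "Covariates in these models will include study arm, recruitment month/season, US region, and demographic factors identified as significantly imbalanced across arms".

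Two design facts set the calendar. Under Reach, section 4.4.1 says that eligibility and enrollment are assessed "over 12-18 months in order to assess reach/potential generalizability". Section 4.3 says that participants are asked to "complete follow-up assessments at 3, 6, and 12 months post-baseline", so each person's visits are timed from that person's own baseline.

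**The concern.** Someone enrolled in late winter has a 3-month change that runs into summer; someone enrolled in late summer has one that runs into winter. Part of the spread in 3- and 6-month changes may therefore reflect the calendar.

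Section 13.1 adjusts for this in the arm comparison, where randomization already balances season in expectation. Section 13.2 omits the adjustment where nothing balances season, because participants choose how much they use the site. The gap exists within a single arm as well as in the pooled correlation.

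Two consequences need to be kept apart:

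- **Dilution.** Seasonal variance in the change score weakens the correlation even if use is unrelated to season.
- **Bias.** If use also varies with enrollment month or season, the raw correlation absorbs part of the seasonal swing. For UV exposure, heavier use among people heading into summer would push the correlation against Hypothesis 4. For protection, if that index also rises into summer, the same pattern would favor the hypothesis.

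At stake is whether a null, reversed or positive Hypothesis 4 result can be separated from enrollment timing.

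**Working it through.** **The plan's own figures.** The plan gives no power or detectable correlation for this analysis. Its nearest design figures reproduce:

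- Retention: 1500 × 0.8 = 1200, × 0.8 = 960, × 0.8 = 768, as stated.
- Detectable effect at 80% power and two-sided 1.25%: (2.498 + 0.842) × √(1/480 + 1/480) = 0.216 (stated 0.22), and with 480 against 240, 3.340 × √(1/480 + 1/240) = 0.264 (stated 0.26).

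**Detectable correlation.** At two-sided 5% and 80% power, ρ = tanh[(1.960 + 0.842)/√(n − 3)]. This gives about 0.13 at n=480 (one large arm at 3 months) and 0.08 at n=1200 (all arms).

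**Inputs.** From section 13.1: n=480, and SD 0.74 for the 3-month change in UV exposure in the prior control arm, used here as the non-seasonal SD at every visit. Assumed, because the documents do not give them: a yearly cosine in the exposure index with amplitude A = 0.25 or 0.50 index units, even accrual over 12 months, and a correlation g between use and the seasonal part of the change.

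**Seasonal share of the variance.** For a lag of L months the seasonal change has variance 2A² sin²(πL/12).

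- L=3: variance A². Share = 0.0625/(0.0625 + 0.5476) = 10%, or 0.25/(0.25 + 0.5476) = 31%.
- L=6: variance 2A². Share = 0.125/(0.125 + 0.5476) = 19%, or 0.50/(0.50 + 0.5476) = 48%.
- L=12: variance 0. The cycle cancels.

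**Expected effect on the correlation.** With no use-season link, the true value shrinks by √(1 − share): −0.13 becomes −0.123 or −0.108 at 3 months, and −0.117 or −0.094 at 6 months. With no true association and g = 0.1, the spurious value is 0.1 × √share: 0.032 or 0.056 at 3 months, and 0.043 or 0.069 at 6 months. Spearman coefficients run slightly smaller.

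**Simulation.** There were 1000 runs per cell, n=480. Raw Spearman is compared with a rank correlation after month means are removed (n − 13 degrees of freedom). Power is for a true ρ of −0.13 with g = 0. False rejection is with no true association and g = 0.1.

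| Change | A | Raw power | Adjusted power | Raw false rejection | Adjusted false rejection |
|---|---|---|---|---|---|
| 3 months | 0.25 | 73% | 78% | 10% | 4% |
| 3 months | 0.50 | 60% | 76% | 22% | 5% |
| 6 months | 0.25 | 68% | 77% | 14% | 5% |
| 6 months | 0.50 | 50% | 78% | 30% | 3% |
| 12 months | 0.25 | 76% | 76% | 5% | 5% |
| 12 months | 0.50 | 78% | 77% | 6% | 5% |

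With g = 0 and no true association, raw and adjusted tests both reject in 4-6% of runs. The simulation standard error is about 1.4 points near 75% (√(0.75 × 0.25/1000)), and repeat runs agree to within a few points. The 6-month rows keep n=480 for comparison; the plan expects 960 × 2/5 = 384 in a large arm by then, so power would be lower for both methods.

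**Accrual pattern.** With enrollment confined to April-June, A = 0.35 and a link of 0.2, the raw test falsely rejects in roughly 8-10% of runs at 3 months. Even accrual at the same link gives 28-68% for A = 0.25-0.50. With April-June enrollment, no link and a true ρ of −0.12, power is about 69% raw and 71% adjusted.

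**The case against.** The strongest objection is that every size above rests on inputs that the documents do not supply: the seasonal amplitude, the use-season link and even accrual. Section 4.1 notes that a consumer panel can deliver enrollment within a set period, so accrual may cluster. This stands, and it is why the sizes are illustrations only. The prior control arm's mean 3-month changes (0.34/0.74 = 0.46 SD and 0.37/0.90 = 0.41 SD) are sizeable, but the documents do not attribute them to season.

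A reader might infer that the planned test has an inflated error rate as it stands. The documents do not support that. Inflation needs use to follow season or enrollment month; without that link the error rate stays near 5% and only dilution remains. A link is plausible: UV4.me2 asks users to log sunbathing and sunscreen use, and recruitment sources may run at different times and bring different users. Neither route is documented.

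A reader might also infer that a real intervention benefit could vanish, or that the bias must work against Hypothesis 4. Neither follows. A use-outcome correlation is not an intervention effect, and the likely direction can differ between the exposure and protection indexes.

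Finally, this is a secondary, non-randomized analysis, and the hypothesis claims association only. That limits the weight of the point. It does not explain why a covariate used for the 3-month changes in section 13.1 is dropped in section 13.2.

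**Conclusion.** The point holds for the 3- and 6-month changes. Section 13.2 tests Hypothesis 4 with a correlation that has no seasonal or regional term, while section 13.1 adjusts the 3-month changes for both.

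Dilution needs only that the change scores vary with season across the enrollment months actually used. Bias and excess false positives need, in addition, a use-season link. Under the assumed ranges, the spurious correlation at a link of 0.1 is about 0.03-0.07, against detectable values of about 0.13 (n=480) and 0.08 (n=1200). An artefact could therefore approach the size of the signal sought, most of all when arms are pooled. The adjusted test recovers fully here partly by construction, because the simulated season depends on enrollment month alone; regional differences were not simulated.

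The point does not extend to the 12-month change, apart from year-to-year differences in season, nor to the randomized primary comparison.

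**What to change.** In section 13.2, make the 3- and 6-month test of use against outcome a partial Spearman correlation, or an equivalent regression of ranked change on ranked use. Adjust for recruitment month/season and US region, and add study arm whenever arms are pooled. State whether month or season enters the model, since section 13.1 leaves that open. Report the raw Spearman coefficient as descriptive. Using the same model at 12 months is harmless but optional.

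The cost is about one sentence of text and roughly 11-15 degrees of freedom out of several hundred (11 of them for month); the covariates are already collected. The adjusted result remains a non-randomized association, open to other confounding such as motivation, and should be reported as such.
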